1.1 Responsibilities

1.2Changes from Protocol

- A secondary endpoint was added for the analgesic treatment efficacy: Patient's daily APS and the linear regression coefficient of its daily evolution
- Secondary objectives of the final study were precised, while they were absent from the protocol

1.3Amendment Rationale

The primary study objective is the prediction of individual analgesic treatment efficacy. All primary and secondary endpoints concerning treatment efficacy were based on differences between weekly average of pain measures at baseline and at the end of the follow-up period. Due to frequent changes in the analysis therapy of cancer patients with bone metastases, it is essential to have a temporal granularity finer than the 4 weeks (i.e. follow-up duration). Therefore an additional endpoint was added for describing the daily values of APS and its linear trend throughout follow-up.

No secondary objective was described in the study protocol. For the sake of clarity, the current analysis plan describes 3 secondary objectives, all of which can be considered as intermediary milestones necessary in order to reach the (unmodified) primary objective of the study.

2 Study objectives

2.1 Primary Objective (for the whole study)

To define predictive factors of pain management/treatments efficacy in cancer patients with bone metastases suffering from pain (or cancer-induced bone pain (CIBP)), based on individual patient disease, therapy history, personality traits and expectation.

2.2 Secondary Objectives

- 1. To identify groups of patients showing similar profile at baseline, in terms of personality traits and disease history
- 2. To measure the concordance between questionnaire-based and clinical pain assessment
- 3. To identify typical evolution of pain level among cancer patients with bone metastases

2.3 Interim Objectives

- 1. To confirm the considered sample size of approximately 140 patients completing this study
- 2. To confirm questionnaires and historical data to be collected

2.4 Primary Endpoint

Individual analgesic treatment efficacy endpoint: patient's change from baseline of pain severity, as measured by the weekly means of the daily Average Pain Scores (APS).

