Diary:	The following information will be collected daily in the diary: APS and Worst Pain Score (WPS) for the past 24-hours, intake of additional to prescribed analgesic treatment (rescue analgesic treatment).
Study Evaluation Criteria and methods:	
Patient general health status	Symptoms related to analgesic treatment will be listed, and if the frequency of symptoms allows, they will be summarized using descriptive statistics.
Pharmacokinetic	Not applicable
Pharmacodynamic	Analysis of subjective changes from baseline of pain severity as measured by the weekly means of the daily APS and WPS, by Brief Pain Inventory (BPI), Investigator Global Assessment of Change (IGAC) and Patient Global Assessment of Change (PGAC), QLQ-C30 will be performed. In addition, analysis of quantitative changes measured by MPA, SA, MDA, MPT and TPS will be performed and compared between enrolment Visit and Visit 2. These tests will be listed and summarized using standard descriptive statistics. Additional analysis will be performed if warranted upon data review
Statistical Analysis:	Both effects on subjective and quantitative measures will be analyzed using Statistical Learning approaches potentially including covariates to be described in the Statistical Analysis Plan (SAP).
Safety:	Not applicable
Exploratory measures:	For patients who give their consent, archived tumor tissue block, if any and/or aliquot of standard safety laboratory blood sample will be used for genotyping exploratory research.
Interim Analysis	A preliminary analysis will be scheduled after approximately 60 patients complete the study

Table of Contents

1. Synopsis.....	3
2. Study Objectives and Endpoints.....	10
2.1. Primary Objective	10
2.2. Primary Endpoint	10
2.3. Secondary Endpoints	10
3. Study Background Information	11
3.1. Investigational Medicinal Product(s) Name(s).....	11
3.2. Introduction - Literature and/or Data Background	11
3.3. Rationale for the Study	15
4. Study Design	16
4.1. Description of Study Design	16
4.1.1. Screening and Enrolment Visit.....	17
4.1.2. Observational Period – Intermediate Phone Call	20
4.1.3. Visit 2: End of Observational Period and Follow-up Visit.....	21
4.2. Rationale for the Study Design	21
4.2.1. Population Selection and Sample Size.....	21
4.2.2. Justification for Study Design.....	22
4.2.3. Interim Analysis	22
5. Population Recruitment, Enrolment and Withdrawal	23
5.1. Definitions	23
5.2. Population Recruitment	23
5.3. Inclusion Disease Criteria.....	23

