10.1.1.1. Analysis Populations

Statistical analysis and data tabulation will be performed using the full patient population unless specified otherwise.

The patients constitute data vectors of potentially all data sources:

- CRF entries,
- Item-level entries from personality questionnaires
- Facet-level summaries from personality questionnaires
- Meta-level summaries from personality questionnaires
- Diary entries
- Meta-level summaries from diary
- Pain evaluations

At any time during the statistical analyses, a subset of those vector entries (thus reducing the population to some of these input features only) might be considered.

In some exploratory analyses, new populations might also be defined, for example based on sub-groups of patients showing similar pain evolution throughout the study.

A special set of features – the target features – characterize the analgesic efficacy and are defined as follows:

- APS difference with respect to baseline (primary endpoint)
- WPS difference with respect to baseline (secondary endpoints)
- BPI difference with respect to baseline (secondary endpoints)
- IGAC difference with respect to baseline (secondary endpoints)
- PGAC difference with respect to baseline (secondary endpoints)
- QLQ-C30 with respect to baseline (secondary endpoints)
- CPAs difference with respect to baseline (secondary endpoints)

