10.1.1.2. General Statistical Procedures

The statistical analyses will be divided into four main parts (P1 to P4): descriptive, univariate, multivariate and exploratory. The descriptive part intends to describe the data by generating a set of statistical summaries of each patient-vector entry. The univariate analysis will investigate the link between each patient-vector entry and the treatment response (as described by the pain evolution). All the statistical procedures will further be described in a dedicated SAP.

P1 - Data Description

P11: Data pre-processing and summary.

Classical statistical information will be computed for each input feature (mean, median, standard deviation). A log-transform will be applied to some features, when appropriate.

P12: Missing values management.

The number of missing values will be reported for each feature. In subsequent analyses, value imputation might be performed if needed. Such cases will be documented.

P13: Outlier detection.

Population outliers will be detected through a Principal Component Analysis (PCA) visualization. Outliers might be removed for at least parts of the further analyses. Such cases will be documented.

P2 - Univariate Analysis

P21: Features Impact Assessment.

The correlation between each feature and the treatment response in terms of target feature will be assessed.

For each test performed in P2, if a non-conclusive p-value is obtained and when possible, an estimation of the required sample size will be performed based on the study data.

P3 - Multivariate Analysis

The aims of the multivariate analysis are i) to explore links between features (including all input and target features), ii) to predict target features based on input features, iii) to identify most important input features for this predictive task.

P4 - Exploratory Analysis

P41 - New populations identification.

We identify subgroups of patients with intra-group similar pain evolution curves, and inter-group different pain evolution curves. We define new “class labels” accordingly. If coherent profiles are found, we might consider applying a modeling procedure similar to P3.

P42 – Genetic data exploitation.

In case the genetic material from patients is used, similar experiments as those described above might be performed to discover links between genetic traits (snips for example) and pain evolution or pain treatments efficacy.

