4.2 Study Participant Characteristics

The following variables will be recorded and may be used as quantitative or classification variables:

- Patient characteristics, measured at V1:
 - Study center
 - Patient's sociodemographic characteristics: age, sex and other demographic characteristics
 - Recent analgesic treatment history
 - Personality questionnaires, at facet- and domain-level: Multidimensional Health Locus of Control Scale (MHLCS, with domains I, C and P), Hospital Anxiety and Depression Scale (HADS), Revised Life Orientation Test (LOT-R) and Expectation.
 - Pain evaluation questionnaires: Douleur Neuropathique en 4 questions (DN4), Neuropathic Pain Symptom Inventory (NPSI), and Pain Catastrophizing Scale (PCS)
- Pain and quality of life assessment, measured at V1 and V2:
 - Brief Pain Inventory (BPI)
 - Quality of Life questionnaire in 30 questions (QLQ-C30), IGAC, PGAC
 - Clinical Pain Assessment (CPA): Static Allodynia (SA), Dynamic Mechanical Allodynia (DMA), Mechanical Pain Threshold (MPT), Thermal Pain Sensitivity (TPS)
- Follow-up from the daily diary and intermediate visit:
 - Daily Average and Worst Pain Score (APS and WPS),
 - Daily analgesic therapy (including rescue medication): number of distinct drugs intaken, number of distinct drug categories intaken
 - Intake of rescue analgesic treatment if any,

Note that the description of analgesic therapy hereabove requires the grouping of drugs into a small number of classes which will be described in the Statistical Analysis Report.

The collection of the values of all these variables and variables derived from them for a single patient is referred to as *the patient-vector* below in the text.

5 Description of the Analyses

The final statistical analysis covers four aspects (Ax) detailed in the following sections:

- A1: Descriptive statistics at baseline, covering secondary objectives number 1 and 2.
- A2: Evolution of daily pain and treatments, covering secondary objective number 3.
- A3: Prediction of treatment efficacy, covering the primary objective

In addition, the interim statistical analysis will cover the following two aspects, corresponding to the interim objectives:

- I1: Sample size computation for the prediction of treatment efficacy.
- I2: Relation between psychological traits and pain evolution

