5.3 A3: Prediction of treatment efficacy

A predictive model will be tuned based on the characteristics at V1 in order to predict the efficacy of each treatment on the patient. One model will be built for each treatment t, with the following design:

- Scope: patients having received treatment t on some but not all days
- Response (target): Per-patient treatment effect, as measured by the average difference of daily APS between the days with and without treatment t
- Predictors: patient characteristics at baseline

The performances of these pre-treatment models will be evaluated inside a resampling procedure. This procedure repeatedly samples 80% data to learn a predictive model whose predictive performances are assessed on the 20% remaining unseen data. In total, 200 train-test splits are performed for each treatment. The predictive model in use will be a ridge regression, as implemented by glmnet::cv.glmnet in R, with parameter alpha=0.

Table (tab-pred-perf) will report the average predictive performance on the test sets for each treatment, in terms of relevant statistics.

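### No analysis in SAP 5 uses the declared primary endpoint as its response; A3, assigned to the primary objective, predicts a different quantity

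*SAP*

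**What the plan says.** The endpoint is stated consistently. SAP 2.4 gives it as "patient's change from baseline of pain severity, as measured by the weekly means of the daily Average Pain Scores (APS"). Protocol 10.1.1.1 lists among its target features "APS difference with respect to baseline (primary endpoint"), and the Protocol synopsis promises "Analysis of subjective changes from baseline of pain severity as measured by the weekly means of the daily APS and WPS".

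Protocol 10.1.1.2 plans to correlate each input feature with the target features (P2), to predict the target features from the inputs (P3), and "iii) to identify most important input features for this predictive task". It then delegates the detail: "All the statistical procedures will further be described in a dedicated SAP".

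The SAP assigns the primary objective to one analysis: "A3: Prediction of treatment efficacy, covering the primary objective". SAP 5.3 defines that analysis by "Scope: patients having received treatment t on some but not all days" and by the response "Per-patient treatment effect, as measured by the average difference of daily APS between the days with and without treatment t".

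SAP 1.2 lists two changes from the protocol: an added secondary endpoint (daily APS and its linear regression coefficient) and the wording of secondary objectives. SAP 1.3 presents the new endpoint as additional and the primary objective as unmodified.

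**The concern.** The protocol leaves it to the SAP to say how the primary endpoint will be analysed, and the SAP names the endpoint but then analyses other quantities. Followed as written, it gives no result on which patient factors predict change in weekly mean APS. The analysis standing in for it has a different target and a different set of patients. The interim decision on patient numbers (I1) is built on that same target, so it too says nothing about how well the declared endpoint can be predicted with 140 completers.

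The definition of the endpoint is also incomplete. Once an analysis of it is added, someone has to choose the baseline and the end week. If that choice is not written down first, it can be made after the data are seen.

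**Working it through.** The documents give no effect size, SD or power for this endpoint, so there is no planned figure to reproduce. The check sets each analysis beside the endpoint and then tests whether the A3 target could serve as a proxy.

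**1. Response variable of each SAP analysis**

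| Analysis | SAP section | Response |
|---|---|---|
| A1 | 5.1 | Baseline variables only |
| A2.1 | 5.2.1 | Mean APS, linear trend, variability around trend |
| A2.2 | 5.2.2 | Daily number of drugs and drug categories |
| A2.3 | 5.2.3 | Linear trend of APS |
| A3 | 5.3 | On-day versus off-day difference in daily APS, per treatment |
| I1 | 5.4.1 | As A3 |
| I2 | 5.4.2 | Linear trend of APS |

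None is change from baseline in weekly mean APS. SAP 5 names eight tables: two of Visit 1 summaries, one of clusters, one of baseline correlations, one each for the distributions of pain and treatment evolution, one of baseline against APS trend, and one of predictive performance. SAP 6.2 lists seven figures. None reports the declared endpoint. The attached table-template file was not available, so the count covers the SAP text only.

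**2. Can the A3 target stand in for the endpoint?** Illustration on assumed values: one patient, 28 diary days, no noise, APS = 6 - 2(d - 1)/27 on day d. Baseline is the Day 1 score of 6. The A3 difference is taken as on-days minus off-days, since SAP 5.3 does not state the direction.

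- Declared change: mean of days 22-28 is 4.222; 4.222 - 6 = -1.78.
- Drug taken on days 1-7 only: 5.778 - 4.741 = +1.04.
- Drug taken on days 15-28 only: 4.481 - 5.519 = -1.04.
- Drug taken every day: there are no off-days, so the target does not exist and the patient is outside the model for that drug. A patient whose whole regimen is constant enters no A3 model.

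The same pain course gives A3 targets of opposite sign, because the on/off difference picks up where the drug days fall on the time trend.

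**3. Which days form the endpoint?**

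- SAP 1.3 refers to baseline and the end of follow-up, and SAP 2.5 to a weekly APS at Visits 1 and 2. Neither gives days or a minimum number of entries.
- The diary runs from enrolment (Protocol 7.2.2.1), so no weekly mean of daily scores exists before it. The only earlier value is WAPS, a single recalled score (Protocol 8.2.4.4).
- Visit 2 is allowed on day 29-43 in the one-visit scenario, and on day 8 + 28 = 36 to day 29 + 42 = 71 in the two-visit scenario (Protocol 8.5.4). The last seven diary days before it therefore run from days 22-28 to days 64-70.
- In the step 2 example, replacing the Day 1 score by the first diary week as baseline changes the result from -1.78 to 4.222 - 5.778 = -1.56.

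**4. Why the added model needs a WAPS-only reference.** Assume baseline and end scores with equal SD and correlation r = 0.7. WAPS alone explains r² = 0.49 of the end score and (1 - r)/2 = 0.15 of the change, with the same residual error. These are values without the entry cut-off, which lowers both. Either way, part of the apparent performance is baseline pain and regression to the mean, not a predictive factor.

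**5. Regression to the mean from requiring WAPS of at least 4.** Expected fall = (1 - r) × SD × φ(a)/(1 - Φ(a)), with a = (4 - mean)/SD and assumed SD 2.

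- Mean 5: 0.51 (r = 0.5), 0.31 (r = 0.7).
- Mean 6: 0.29 (r = 0.5), 0.17 (r = 0.7).

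**The case against.** Several points on the other side are fair.

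- **The A3 target does not come from nowhere.** A reader might infer that the primary endpoint was silently swapped for an unrelated quantity. The documents do not support that. SAP 5.3 states the target openly. SAP 1.2, 1.3 and 2.5 add daily APS as well as its slope, and SAP 1.3 gives the reason: therapy changes often, so finer time resolution is wanted. The A3 contrast derives from that listed secondary endpoint. What stands is that the contrast itself is not listed in SAP 2.4-2.5, and that nothing says it replaces the primary endpoint.
- **The windows are not wholly open.** The endpoint is tied to Visit 1 and Visit 2, and WAPS is the natural weekly score at Visit 1. What is missing is the days, the minimum number of entries and an explicit choice of WAPS. While no analysis uses the endpoint, these gaps affect no planned result; they matter once one does.
- **The slope is related to change.** A reader might infer that it is badly misleading. On assumed exponential curves with nearly the same declared change (-1.8 to -2.0), it runs from -0.063 to -0.041 per day over 28 diary days, a 1.5-fold range with the same sign. An 8-fold range appears only when extreme combinations of half-life and follow-up length are compared. The slope remains a declared secondary endpoint, not the primary one.
- **The study is observational, with no hypothesis test behind its size.** True, but the provision for additional exploratory analyses cannot supply the analysis of a declared primary endpoint.

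**Conclusion.** The mismatch is real and should be resolved before database lock. No analysis, named table or figure in the SAP text addresses the declared primary endpoint, and the analysis assigned to the primary objective, together with the interim sample-size step, uses a target that can differ from it in sign and excludes patients on constant treatment. This rests on reading the SAP text alone. The +1.0, -1.0 and -1.8 figures are an illustration on one assumed curve, not an estimate of how often the two disagree in this population.

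It does not follow that A3 is worthless. It addresses a treatment-specific question that a model of overall pain change does not. The fault is that it occupies the place of the primary analysis without being declared as such.

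**What to change.** In SAP 5, add a primary analysis of the declared endpoint.

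- **Response:** change from WAPS to the mean diary APS over the last seven days before Visit 2, with a stated minimum number of scored days.
- **Model:** one ridge regression with the A3 resampling settings (200 splits, 80% training), WAPS as an unpenalised covariate and the Visit 1 characteristics as predictors.
- **Reporting:** the coefficients, and test performance as the reduction in RMSE over a WAPS-only model in the same splits.
- **A2.3:** run it also on this endpoint, as WAPS-adjusted partial correlations with BH correction.
- **I1:** base the learning curve on the same gain over WAPS alone. This must be settled before the interim transfer to be of use there.
- **Sensitivity:** Visit 1-day APS as baseline; and a fixed window of days 22-28 that includes drop-outs with those data. In the two-visit scenario Visit 1B can fall as late as day 29, so its questionnaires may be missing or later than that window.
- **Secondary:** keep the slope and the per-treatment A3 models.

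The alternative is to declare and justify in SAP 1.2, before database lock, that the A3 target replaces the primary endpoint, and to change 2.4 to match.

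A separate, smaller correction is to add primary-disease and cancer-treatment history to the variable lists in SAP 4.2 and 5.1. Both are collected, and the objectives in SAP 2.1 and 2.2 name patient disease and disease history.

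The cost is SAP wording, one model, one further A2.3 run and their tables, with no new data. The limits should be stated: WAPS is a single recalled item and also the entry criterion, so mean change includes regression to the mean (about 0.17 to 0.51 points under the assumptions above). Analysing completers leaves selection by drop-out, which the fixed-window sensitivity covers only in part. The pooled model predicts pain course under usual care, not the effect of a given treatment.

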2.5 Secondary Endpoints

- Individual analgesic treatment efficacy: Patient's daily APS and the linear regression coefficient of its daily evolution
- Individual analgesic treatment efficacy: Patient's change from baseline of
 - Pain severity, as measured by the weekly means of the daily Worst Pain Score (WPS),
 - Pain severity and interference as measured by the Brief Pain Inventory (BPI),
 - Investigator and Patient Global Assessment of Changes (IGAC and PGAC),
 - Pain intensity measured after Clinical Pain Assessments (CPAs) at Visit 2,
 - Quality-of-Life Questionnaire in 30 questions (QLQ-C30).
- Correlation between pain severity and clinical pain assessment as measured by:
 - Pain severity, as measured by the weekly Average Pain Score (APS) at Visit 1 and 2,
 - Pain intensity measured after Clinical Pain Assessments (CPAs) at Visit 1 and 2.

Variables used as predictive factors rather than as endpoints are described hereunder in Section 4.2.

3 Summary of Study Design

See the latest protocol version.

4 Populations for Analyses

Statistical analysis and data tabulation will be performed using the population of completers unless specified otherwise. This set includes all data from patients who have been screened, included and who completed the study (no drop-outs).

For the interim analysis, only patients who completed the study before the interim database transfer will be included.

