5.3. INCLUSION DISEASE CRITERIA

Patients are eligible to be included into the study if they meet all of the following CIBP disease diagnosis criteria:

- [1] Patients with bone tumors or bone metastasis from any primary cancer origin that is supported by histological or radiological investigations.
- [2] Patients having been or being treated for their bone metastasis and/or their primary cancer.
- [3] Patients who require analgesic treatment for unsatisfactory pain relief.
- [4] Patients will be required to score at least 4 on the WAPS 11-point NRS during the week preceeding enrolment.
- [5] Patients undergoing or not a radiotherapy program provided visit procedures are performed before any radiotherapy sessions if scheduled on the same visit days.

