5.1 A1: Descriptive statistics at baseline

This section provides general information useful before starting any data analysis. Only variables at baseline are analysed at this point, so that any decisions taken are not influenced by the observed response to treatment. The variables covered are: sociodemographic characteristics, recent analgesic treatment history, personality questionnaires, pain (including CPA) and quality of life at visit 1.

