5.1.3 A1.3: Outlier detection and clustering

Population outliers will be detected through a principal component analysis (PCA) visualization, reported in Figure (1). The percentage of variance captured will be documented. The patients will be colored by their study center in order to detect possible differences among the centers.

Outliers might be removed for at least parts of the further analyses. Such cases will be documented.

A clustering procedure, namely an ensemble k-Means, will be applied in order to identify subgroups of patients with intra-group similar variables at baseline, and inter-group different variables at baseline. Table (tab-v1-clustering-desc) will report per-cluster univariate statistics (median, first and third quartiles) for all variables used in the clustering procedure.

A1.4: Correlation analysis 5.1.4

The correlation between each variable (personality traits and sociodemographic variables) and the pain at baseline (APS, WPS, BPI severity, interference and QLQ-C30) will be assessed. Statistical tests for non-zero Spearman's correlation will be used. For categorial variables, exact Fisher tests will be used. Correction for multiple testing will be applied. Results will be reported in Table (tab-v1-correlations) and Figure (2). Scatterplots of the significant correlations will be produced. Figure (3) will detail the correlations within pain assessment variables and Figure (4) the correlations between personality traits and pain assessment.

5.2A2: Evolution of daily pain and treatments

Pain evolution will first be analysed on its own (secondary objective 3, i.e. without linking it to the evolution of treatments). Then, the evolution of analgesic therapies are studied, as well as their correlation with pain evolution. Due to the complexity of treatments combinations for each patient and their frequent adaptation during the follow-up period, this analysis will be made on a simple summary of the therapy evolution. Finally, the interest of each variable characterizing the patient at baseline is evaluated for its relation with the pain evolution profile.

A2.1: Summary of individual pain evolution 5.2.1

Feature extraction will be performed in order to summarize each per-patient APS evolution curve into 3 meaningful variables:

- mean APS value
- linear trend of APS
- variability of APS around trend

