6.2 Figures

Figure 1: Outlier detection by Principal Component Analysis based on data at baseline. The two first components are represented (Variance captured: %). Colors indicate the grouping of points into clusters.

Figure 2: Matrix of correlations between all pairs of variables at baseline (personality traits and sociodemographic variables)

Figure 3: Scatterplots of the significant correlations between the different pain measures at baseline

Figure 4: Scatterplots of the significant correlations between a personality trait and a pain measure at baseline

Figure 5: Summary visualization of the evolution of pain during follow-up period. Each point represents a patient, with average APS as abscissa and linear trend as ordinate

Figure 6: Summary visualization of the evolution of analgesic treatments during follow-up period. Each point represents a patient, with the number of different analgesic drugs (for the graph on the left) or the number of different analgesic drug classes (on the right) as abscissa, and their linear trend as ordinate

Figure 7: Learning curve for the prediction of analgesic treatment efficacy. The average performance evaluated by cross-validation on random subsets of the data is shown in ordinate, with the size of the training set as abscissa. An extrapolation curve (LOWESS) is also shown for sample sizes up to N=200.

7 Data Transfer and Unblinding Plan

The study data is collected and managed by Aepodia SA. Several information transfers will occur between Aepodia and DNAlytics, under the supervision of Tools4Patient:

Jun. 2015 **Database table structure transfer** – The objective of this transfer is to allow DNAlytics to prepare the analysis scripts and finalize the SAP. The data concerning a few included patients will be transfered in order to make the scripts creation possible. Those patients data are anonymized by Aepodia prior to the transfer to DNAlytics. Those patients will however be identified by their inclusion number.

	T2001-01 – Statistical Analysis Plan	
DNAIUtics Deterdriven personalized medicine from R&D to market access		To : T4P Auth. : [name] V1.3 - 2017-04-10

May 2017 (Est.) Interim database transfer – The objective of this transfer from Aepodia to DNAlytics is to apply the interim analysis plan described in this document. Those patients data are anonymized by Aepodia prior to the transfer to DNAlytics. Those patients will however be identified by their inclusion number.

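### The APS–CPA correlation is declared for Visits 1 and 2, but its assigned analysis is baseline-only, does not name CPA, and describes only a figure of significant pairs

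*SAP*

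**What the plan says.** Secondary objective 2 (SAP 2.2) is "To measure the concordance between questionnaire-based and clinical pain assessment". SAP 2.5 gives its endpoint as a correlation with two sides: "Pain severity, as measured by the weekly Average Pain Score (APS) at Visit 1 and 2", and "Pain intensity measured after Clinical Pain Assessments (CPAs) at Visit 1 and 2". Both sides name both visits.

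The overview in SAP 5 allocates the objective: "A1: Descriptive statistics at baseline, covering secondary objectives number 1 and 2". SAP 5.1 then limits that block: "Only variables at baseline are analysed at this point". The stated reason is that decisions taken there should not be influenced by response to treatment.

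Within A1, section A1.4 correlates personality and sociodemographic variables with pain: "the pain at baseline (APS, WPS, BPI severity, interference and QLQ-C30) will be assessed". CPA is on neither side. The A1.4 text says that Figure 3 covers correlations among the pain assessment variables. Its caption in SAP 6.2 is narrower: "Scatterplots of the significant correlations between the different pain measures at baseline". The Figure 2 matrix is captioned for personality and sociodemographic variables.

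On entry, Protocol 5.3 states: "Patients will be required to score at least 4 on the WAPS 11-point NRS during the week preceeding enrolment". Protocol 8.2.4.4 describes the WAPS as one rating of the past week, asked before enrolment. The ordinary APS covers the last 24 hours.

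**The concern.** The declared endpoint and the analysis assigned to it do not match. An analyst who follows the SAP would report nothing on APS–CPA concordance at Visit 2, although both kinds of data are collected then.

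At Visit 1 the analyst would have no instruction to correlate CPA with APS beyond a figure whose caption keeps only significant pairs. Weak correlations are as much an answer to a concordance question as strong ones. A display that drops the weak ones and keeps the chance-high ones makes agreement look better than it is.

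**Working it through.** The documents give no power or precision figure for this endpoint (Protocol 4.2.1 says the sample size rests on neither), so there is nothing to reproduce. The check has three parts.

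**1. Tracing the endpoint to an analysis**

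| SAP section | Visit 1 APS–CPA correlation | Visit 2 APS–CPA correlation |
|---|---|---|
| 2.5 (endpoint) | declared | declared |
| 5 and 5.1 (A1) | in scope; CPA at Visit 1 is listed | excluded by the baseline rule |
| A1.4 | CPA not named; Figure 3 only | none |
| A2.1–A2.3 | none | none (APS trend, drug counts, baseline features against trend) |
| A3 | none | none (ridge prediction of treatment effect) |
| I1, I2 | none | none (learning curve; baseline features against trend) |

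The Visit 2 column is empty after the first row.

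**2. What a significant-only display does**

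Inputs: n = 140 completers (SAP 2.3) and two-sided alpha 0.05 (SAP introduction). True correlations of 0.10 and 0.20 are assumed.

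- Smallest significant correlation: |r| = t/√(n − 2 + t²). With t = 1.977 on 138 degrees of freedom, this is 1.977/√(138 + 3.91) = 0.166.
- Sampling model: Fisher z, with mean atanh(ρ) and standard error 1/√(n − 3) = 1/√137 = 0.085. I simulated from this and kept results beyond 0.166.

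| True correlation | Chance of being shown | Mean absolute value when shown |
|---|---|---|
| 0.10 | 22% | 0.21 |
| 0.20 | 66% | 0.24 |

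A1.4 also applies a multiplicity correction without naming the method or the family. Under Bonferroni with an assumed 25 to 50 pairs, the threshold rises to about 0.26 to 0.28, so a true 0.20 could be shown only if overestimated.

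For comparison, unfiltered estimates at n = 140 have these 95% intervals, tanh(atanh(r) ± 1.96/√137):
- r = 0.20: 0.04 to 0.35
- r = 0.30: 0.14 to 0.44
- r = 0.40: 0.25 to 0.53

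**3. Range restriction at Visit 1 (illustrative)**

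Assumptions, none of them in the documents: unrestricted weekly pain is normal with mean 4, 5 or 6 and SD 2, rounded to 0–10; its latent correlation with CPA is 0.3, which gives a Spearman value of about 0.28. Power is for an uncorrected test at n = 140 and is about 93% without restriction.

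| Visit 1 score | Spearman after the entry rule | Power |
|---|---|---|
| Recalled WAPS itself (cut directly at 4) | 0.18, 0.21, 0.24 (mean 4, 5, 6) | about 58% to 82% |
| A score correlating 0.7 with WAPS (cut indirectly) | 0.24 to 0.27 | about 81% to 89% |

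The normal model is rough: SA, DMA and TPS are rated only if painful, and MPT comes from seven filaments (Protocol 8.2.1). The direction is sound; the size is only indicative.

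**The case against.** **Is the output really filtered?** The A1.4 text on Figure 3 has no significance filter; only the caption does. SAP 5.1 counts CPA within baseline pain, and SAP 6.1 refers to a file of table templates that is not among the documents. A full pain-by-CPA table may exist there. This stands: the text does not specify one, but its absence cannot be asserted. It does not touch the Visit 2 gap.

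**Could the protocol fill the gap?** Its synopsis compares CPA between enrolment and Visit 2, and its section 10.1.1.2 speaks of exploring links between features. The first concerns change over time. The second is too general to count as a planned Visit 2 correlation.

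**Does it matter enough?** SAP 1.3 treats the secondary objectives as intermediate steps, and no confirmatory claim depends on this correlation. That limits the consequence, but a declared endpoint should still have an analysis.

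**A stronger reading to resist.** A reader might infer that the entry rule biases Visit 1 concordance towards zero, so that Visit 2 should be the main estimate. The documents do not support this.

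- The cut at 4 falls directly on the recalled WAPS. The APS completed at site at Visit 1 is a 24-hour rating and can be below 4. The SAP does not say which score it means by weekly APS at Visit 1.
- A Visit 1 correlation is not biased for the population the study enrols. It is low only relative to an unrestricted pain range, to which no objective refers.
- Visit 2 holds the same selected patients. It is less affected (assuming a correlation of 0.5 between the visits' scores, about 0.28 becomes about 0.27), but it has its own complications. No WAPS is scheduled there, and under Protocol 8.2.1 a changed most painful area leads to CPAs on two areas.
- SAP 2.5 gives the two visits equal standing.

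**Conclusion.** The concern holds as a mismatch between endpoint and analysis. From the SAP text alone, with no assumption, the Visit 2 APS–CPA correlation has no planned analysis and the Visit 1 correlation is not properly specified.

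If Figure 3 as captioned is the only output, the displayed values would average about 0.21 for a true 0.10 and 0.24 for a true 0.20. Those figures assume 140 completers, no multiplicity correction and no fuller table in the template file.

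Range restriction at Visit 1 merits a caveat, conditional on the recalled WAPS being the score used. It is not a reason to demote Visit 1. Nor do the documents establish that discordant pairs would be hidden, because the A1.4 text is wider than the caption and the templates are unavailable.

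**What to change.** 1. In A1.4, name CPA and tabulate the Spearman correlation with 95% CI for every pair of weekly APS with a CPA measure (SA, DMA, MPT, TPS) at Visit 1, whatever the p-value.
2. Add the same table for Visit 2 outside the baseline-only block, for example under A2, so that the A1 rule stays intact. Keep the two visits on equal footing.
3. State which weekly score is used at each visit: the recalled WAPS or a diary mean, and over which days. The diary starts only at enrolment, so the two visits may rest on different kinds of score.
4. State which painful area supplies the Visit 2 CPA value when the most painful area has changed.
5. If the WAPS is the Visit 1 score, note beside the table that entry restricts it to 4 or more, which lowers the correlation relative to an unrestricted range.

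The cost is one or two tables and a few lines of SAP text. CPAs are already done at enrolment and Visit 2, and the diary APS runs until Visit 2, so no new data are needed.
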